2.4 Rationale

Patients who have mastectomy and reconstructive surgery often experience discomfort from not only the surgical incisions, but also from the drainage tubes inserted at the incision sites. The tubes and drainage receptacles are often difficult to manage when patients are discharged from the hospital, wearing typical clothing and returning to regular daily activities.

Most women are able, at the time of mastectomy, to have breast reconstruction surgery to rebuild and contour breast shape. Post-operative care is more complex than mastectomy alone and requires an inpatient stay of two to four nights. The accumulation of fluid – a *seroma* – is a frequent complication following breast surgery and warrants the insertion of drainage tubes for prevention. In a review investigating techniques in the prevention and management of seromas after breast surgery, drains produced a significant reduction in seroma incidence.⁷ The number of drains depends on the type of surgery and preference of the surgeon and ranges from 2 for unilateral and from 4 for bilateral mastectomy.^{8,9} Patients after mastectomy and breast reconstruction experience soreness in the chest, underarm and shoulder, as well as numbness at the drainage site. Patients have reported the greatest discomfort at the drain insertion sites. The number of drains after mastectomy has also been associated with increased pain in the post mastectomy patient, although the number of drains was not associated with the rate or number of seromas.^{8,10} If axillary lymph nodes are removed, patients may experience some numbness in the arm and also are at risk for *lymphedema*,¹¹ a build-up of lymph that causes swelling in the arm, hand, breast, underarm, chest, trunk and/or back.

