5.1.3 Instruments Measuring Study Outcomes

Participants will complete study questionnaires self-reporting pain, pain management, breast symptoms and health related quality of life at three time points (see section 10, Study Calendar). Questionnaires will be answered using pen and paper in the hospital on the first (or second) day post-surgery (T1), at home (T2), or in follow-up clinic after all drains are removed (T3). If participants cannot answer the T3 questionnaire in clinic, a research coordinator will contact the participant to administer the questionnaire within 24 hours of the follow-up appointment via telephone interview or secure file exchange (using the Partners Biscom Delivery Server). Instruments are the following:

Demographic questionnaire (T1)

The questionnaire includes age, language spoken at home, ethnicity, race, marital status, education, and occupational status.

Pain Intensity Numeric Scale (PINS) (T1, T2, T3)

The PINS measures pain intensity with a single item, on a 0-10 scale and is in common clinical use.

Pain Frequency and Pain Intensity Distress (Symptom Distress Scale) (T1, T3)

Two items from the Symptom Distress Scale^{25,26} measure pain frequency and pain intensity in the past week, on a 5-point scale.

Patient-Reported Outcomes Measurement Information System (PROMIS®) Pain Intensity (T1, T3)

This 3-item instrument from the PROMIS item bank²⁷ measures pain intensity over the past week and right now, on a 5-point scale (PROMIS Item Bank v.1.0 – Pain Intensity – Short Form 3a).

Patient-Reported Outcomes Measurement Information System (PROMIS®) Pain Interference (T3)

This 8-item instrument from the PROMIS item bank²⁷ measures the interference of pain with daily activities and social relations, on a 5-point scale (PROMIS Item Bank v.1.0 – Pain Interference – Short Form 8a).

Pain Management (T2)

Participants will keep a daily pain diary between hospital discharge and follow-up clinic appointment (the T2 period) to document pain intensity, use of pain medications, and whether and how long they wear post mastectomy garments each day.

EORTC QLC-C30 (T3)

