13.2 Sample Size, Accrual Rate and Study Duration

The primary objective of this study will be to compare pain intensity (measured on the 0-10 scale, PINS) at the follow-up clinic appointment when all drains are removed (T3) between those randomized to UC or Jacki groups. A reduction of 1.0 on the PINS is thought to be clinically significant. With a sample size of 130 there is 80% power to detect a 1-point difference in PINS between UC and Jacki groups using a Wilcoxon rank sum test at the 2-sided 0.1 significance level assuming a standard deviation of 2.2 from

the preliminary study. The following table depicts the impact on power if the standard deviation at the follow-up visits is smaller or larger than estimated.

Standard Deviation	Power
1.8	91%
2.0	86%
2.2	80%
2.4	74%
2.6	68%

With a projected 13% rate of attrition, a total of 149 participants enrolled will yield an analytic sample of 130 evaluable participants. This number of participants will be accrued and will complete data collection within 10 months, based on clinical volume .

Accrual Targets				
Ethnic Category	Sex/Gender			
	Females	Males	Total	
Hispanic or Latino	39	+ 0	=	39
Not Hispanic or Latino	91	+ 0	=	91
Ethnic Category: Total of all subjects	130	+ 0	=	130
Racial Category				
American Indian or Alaskan Native	0	+ 0	=	0
Asian	6	+ 0	=	6
Black or African American	13	+ 0	=	13
Native Hawaiian or other Pacific Islander	0	+ 0	=	0
White	111	+ 0	=	111
Racial Category: Total of all subjects	130	+ 0	=	130

No interim analyses are planned due to the short duration, minimal risk, and minimal burden of the study. There are no early stopping rules.

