13.5 Analysis of Primary Endpoints

All randomized patients will be included in all analyses. Minimal missing data is expected; therefore, in the event of missing data, no imputation will be performed. The analyzable sample for the primary endpoint includes participants who are randomized and have reported a pain score at T3 regardless of intervention use. The primary endpoint is pain intensity measured on the 0-10 scale at the follow-up clinic appointment (T3). The pain score will be summarized at each time point and plotted. The T3 pain score will be compared between UC and Jacki groups using a Wilcoxon rank sum test. Due to the nature of the pain measure (i.e., integers on a 0-10 scale), there will be ties in pain score, and the number of ties could affect the performance of the non-parametric test.

Depending on the structure of the data, a t-test may be considered with a possible transformation. Assumptions will be examined and a method selected prior to testing.

Additionally an analysis of covariance (ANCOVA) approach may be considered. Factors that may be associated with the T3 pain score (baseline score, time since discharge, unilateral vs bilateral mastectomy, number of post-surgical drains, neoadjuvant chemotherapy, axillary lymph node dissection, pain management at home with pain medication, and post mastectomy clothing) will be assessed univariately and then adjusted in a multivariable model. The change in pain over time will also be evaluated using linear mixed models.

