13.6 Analysis of Secondary Endpoints

Other secondary endpoints include other pain measures, breast cancer symptoms, and HRQOL which will be measured as described in sections 5 and 10. Scoring and handling of missing data will follow the user manual for the EORTC QLQ-C30 and QLQ-BR23. Analyses conducted at the final time point will be consistent with the analyses described in section 13.5. The change from discharge (T1) to follow-up (T3) will also be evaluated for all secondary measures that are measured at both timepoints.

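### The primary test of T3 pain makes no use of the T1 score or the stratification factors; a prespecified adjusted comparison would recover efficiency at almost no cost

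*Combined protocol and SAP*

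**What the plan says.** Section 13.5 sets the primary comparison: "The T3 pain score will be compared between UC and Jacki groups using a Wilcoxon rank sum test". It allows a t-test, possibly after transformation, as a substitute. Neither test has a covariate or a stratification term.

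Adjustment is optional: "Additionally an analysis of covariance (ANCOVA) approach may be considered". The candidate factors begin with the baseline score and include laterality and number of drains, but also pain medication at home and post mastectomy clothing. They are to be assessed univariately and then put into a multivariable model. Enrolling hospital is not listed. Linear mixed models for pain over time are also planned.

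The pain item is scheduled at all three time points (5.1.3: "Pain Intensity Numeric Scale (PINS) (T1, T2, T3"; also the calendar in section 10). Section 5.1.2 starts the treatment period at hospital discharge, after T1. Section 13.3 stratifies randomisation by hospital and laterality. Section 2.4 names a further pre-treatment factor: "The number of drains after mastectomy has also been associated with increased pain in the post mastectomy patient".

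For secondary measures, 13.6 applies the methods of 13.5 at the final time point and adds: "The change from discharge (T1) to follow-up (T3) will also be evaluated for all secondary measures that are measured at both timepoints".

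The sample size in 13.2 reads "With a sample size of 130 there is 80% power to detect a 1-point difference in PINS between UC and Jacki groups". That figure is for the rank sum test with a two-sided alpha of 0.10 and an SD of 2.2 taken from the sponsor's earlier survey. It uses no T1-T3 correlation.

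**The concern.** When a pre-treatment measure of the outcome is already in hand, leaving it out of the primary comparison gives up precision whenever it correlates with the outcome. Here it is the identical item, and two further pre-treatment factors were thought important enough to stratify on.

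The optional ANCOVA does not close the gap. It is not the primary analysis and need not be done. Univariate screening leaves the final model dependent on the data. Home pain medication and clothing arise after randomisation, and the clothing recorded in the diary includes the jacket itself, so adjusting for them could remove part of the effect under study.

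At stake are some power in the significance test and the width of the interval for the difference, with the same 130 evaluable women. The planned power has little slack: the table in 13.2 falls to 74% at SD 2.4 and 68% at SD 2.6.

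**Working it through.** **Inputs.** From 13.2: N = 130 evaluable, difference 1.0, SD 2.2, two-sided alpha 0.10 (z = 1.645). Assumed: 1:1 allocation, so 65 per arm (the ratio is not stated), and r, which the documents do not give.

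**1. The plan's own figure.** Noether's formula for the rank sum test is power = Φ(√(3N)·|p − 0.5| − 1.645), with p = Φ(1/(SD·√2)). At SD 2.2, p = Φ(0.321) = 0.626. Then √390 × 0.126 = 2.49, and Φ(2.49 − 1.645) = 80.1%. At SD 1.8, 2.0, 2.2, 2.4 and 2.6 the results are 91.5, 86.1, 80.1, 74.0 and 68.1%, against 91, 86, 80, 74 and 68% stated. Every row reproduces.

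**2. Effect of adjusting for T1, by formula.** The residual SD is 2.2·√(1 − r²). With SE = residual SD × √(2/65), power = Φ(1/SE − 1.645) and the 90% half-width is 1.645 × SE.

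| r | Residual SD | Power | 90% half-width |
|---|---|---|---|
| 0 | 2.200 | 82.8% | 0.635 |
| 0.2 | 2.156 | 84.1% | 0.622 |
| 0.3 | 2.099 | 85.8% | 0.606 |
| 0.5 | 1.905 | 91.1% | 0.550 |

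The row r = 0 is the fair comparator, because it is an unadjusted test of the same normal-theory type. Against it the gain is 1.3, 3.0 and 8.3 points. Comparing with the stated 80% would also count the difference between the Wilcoxon and normal-theory calculations.

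**3. Simulation on rounded 0-10 scores.** 3,000 trials per setting, T1 mean 4.98, shift 1.0. Entries are for a usual-care T3 mean of 4.98 / 3.0.

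| r | Wilcoxon | Rank ANCOVA | ANCOVA |
|---|---|---|---|
| 0 | 80.1 / 79.8% | 79.7 / 79.7% | 81.0 / 80.8% |
| 0.3 | 81.6 / 80.9% | 84.5 / 82.2% | 85.9 / 83.8% |
| 0.5 | 80.4 / 79.3% | 88.4 / 86.7% | 90.0 / 88.1% |

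The gain over Wilcoxon is 1.3 to 4.3 points at r = 0.3 and 7.4 to 9.6 at r = 0.5. At r = 0.2 it is about 1 point for rank ANCOVA. With no true effect (r = 0.5), all three tests reject in about 10% of trials, so adjustment does not inflate type I error.

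**4. The 1.0-point rule in 13.7.2.** Efficacy needs a significant difference of at least 1.0. Unadjusted, a difference of about 0.635 is already significant, so the 1.0 threshold is what binds. If the true difference is 1.0, an unbiased estimate reaches 1.0 in about half of trials whatever its standard error; truncation at zero lowers this somewhat. Simulated with a usual-care mean of 3.5 or 5 and r of 0.2, 0.3 and 0.5, the rule is met in 40 to 49% of trials with Wilcoxon plus the raw difference, and in 38 to 48% with rank ANCOVA plus the adjusted difference. Adjustment adds nothing to that decision at the design effect.

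**5. Laterality.** The preliminary survey (2.5) gives 5.26 (SD 2.28) for bilateral and 2.5 (SD 2.13) for single mastectomy, with 60% bilateral. Taking the remaining 40% as single, the between-group variance is 0.6 × 0.4 × 2.76² = 1.83. The within-group variance is 0.6 × 2.28² + 0.4 × 2.13² = 4.93. The share explained is 1.83/6.76 = 27%. That is pain just before discharge, and not only in reconstruction patients, so it does not fix the share at T3. It does support including laterality.

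**6. Change scores (13.6).** With equal SDs, the variance factors are 1 for T3 alone, 2(1 − r) for change and 1 − r² for T3 adjusted for T1. At r = 0.3 these are 1, 1.40 and 0.91. Change is less precise than T3 alone whenever r is below 0.5, and never more precise than adjusted T3.

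**The case against.** The strongest reply is that the plan meets its 80% target unadjusted and that the size of any gain is unknown. T1 is one or two days after surgery, and T3 is usually 7-14 and up to 42 days after discharge, so r may be low. At r = 0.2 the gain is about 1 point. This stands as a limit on size. It does not reverse the direction: at r = 0 nothing is lost beyond simulation error.

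A second reply concerns T1 itself. Section 5.1.1 describes receipt of the assignment before T1 collection, and the arms are not masked, so T1 might be reported knowing the arm. Participants may also skip items, so T1 is scheduled for all but not assured. Both points stand and shape the fix.

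Four stronger readings are tempting, and the documents do not support them:

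- **The trial is underpowered.** Every row of the power table reproduces for the unadjusted test.
- **The plan ignores baseline pain.** Section 13.5 names the baseline score for the ANCOVA and plans mixed models. The question is which analysis is primary.
- **Adjustment makes a positive efficacy finding more likely.** The gain applies to the significance test, not to the 1.0-point criterion at a true 1-point effect.
- **Section 13.6 commits to weak change-score tests.** Change is additional to the T3 analysis and no test is named for it, so no power figure can be attached to it.

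**Conclusion.** The point holds as lost efficiency. It is not an error in the sample size or in the validity of the primary test. For the significance test the gain is about nil at r = 0, 1 to 4 points at r = 0.2 to 0.3 and 7 to 10 points at r = 0.5. The 90% half-width falls from 0.635 to 0.606 at r = 0.3 and to 0.550 at r = 0.5.

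These figures assume 65 per arm, SD 2.2 at both time points, a 1-point shift and a T1 score unaffected by the arm. They credit adjustment for T1 alone; any gain from laterality or hospital is not quantified. The value of r is an assumption throughout, and the documents cannot settle it.

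**What to change.** In 13.5, prespecify one baseline-adjusted primary comparison of T3 PINS, either ANCOVA or rank ANCOVA. Fix the terms as arm, T1 PINS, unilateral versus bilateral mastectomy and enrolling hospital, with number of drains optional but decided in advance. Drop univariate screening and exclude post-randomisation covariates.

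Also:

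- State that the ANCOVA adjusted mean difference, with its interval, is the estimate judged against 13.7.2.
- Keep the unadjusted Wilcoxon as a sensitivity analysis, shown beside the primary result.
- In 5.1.1, state that T1 is completed before the arm is disclosed to the participant.
- Amend the no-imputation sentence in 13.5 so that a missing T1 covariate may be filled with the overall T1 mean, ignoring arm. No woman with a T3 score is then dropped.
- In 13.6, for measures taken at both T1 and T3, analyse T3 adjusted for T1 and keep the T1-to-T3 change as descriptive.

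The cost is wording, settled before outcome data are examined, plus one rule on the order of steps at enrolment. No new data are needed. The remaining downside is that T1 may be influenced by knowledge of the arm if it is collected after assignment, which is why the unadjusted result stays in the report.

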13.7.2 Evaluation of the Primary Efficacy Endpoint

Efficacy will be established if a statistically significant difference of 1.0 or greater on the PINS is detected.

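### The primary test is left to a data-dependent choice with no rule, ignores the randomization strata, and gives no named estimator for the 1.0-point efficacy rule

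*Combined protocol and SAP*

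**What the plan says.** Section 13.2 gives the basis of the design: "With a sample size of 130 there is 80% power to detect a 1-point difference in PINS between UC and Jacki groups". That figure is for the Wilcoxon test, two-sided at 0.10, with SD 2.2.

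Section 13.5 confirms the test: "The T3 pain score will be compared between UC and Jacki groups using a Wilcoxon rank sum test". It warns that ties on the integer scale could affect the test's performance, then continues: "Depending on the structure of the data, a t-test may be considered with a possible transformation". The next sentence is "Assumptions will be examined and a method selected prior to testing". A separate paragraph says that ANCOVA may be considered in addition, with eight candidate factors.

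Section 13.7.2 sets the decision rule: "Efficacy will be established if a statistically significant difference of 1.0 or greater on the PINS is detected". It names neither the test nor the estimator.

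Sections 5.1.1 and 13.3 stratify randomization by hospital and by unilateral versus bilateral mastectomy. The primary test in 13.5 uses neither factor. Section 13.6 makes the final-time-point secondary analyses follow 13.5, so the same open choice carries over to them.

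**The concern.** There are three gaps in the primary analysis.

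- **Choice of test.** The t-test may replace the Wilcoxon test because of what the outcome data look like. No threshold for ties or skewness is set, and the person choosing need not be blinded. A reader of the results could not tell a principled choice from a convenient one, and the significance level is already 0.10.
- **Scale of the effect.** The efficacy rule is in PINS points. A t-test on transformed scores does not estimate a difference in PINS points, and a rank sum test does not estimate a mean difference at all.
- **Strata.** Section 2.5 reports mean pain of 5.26 after bilateral and 2.5 after single mastectomy. If a gap of that kind persists at T3, a test that ignores a balanced, strongly prognostic stratum overstates the variance of the comparison. It is then conservative and loses power.

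**Working it through.** **Inputs from the documents.** Analysed N = 130, difference 1.0, SD 2.2, two-sided alpha 0.10 (13.2); 60% bilateral, means 5.26 and 2.5 (2.5). **Assumed:** 1:1 allocation (65 per arm), the T3 score shapes, the T1–T3 correlation, square-root and log transformations, 2 or 4 hospitals, and the size of the T3 gap between strata.

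**1. The plan's power.** Noether's formula: power = Φ(√(12·N·0.25)·(p − 0.5) − 1.645), with p = Φ(δ/(SD·√2)). At SD 2.2, p = Φ(1/(2.2·1.414)) = 0.626. Then √390 × 0.126 − 1.645 ≈ 0.845, so power is 80.1%. For SD 1.8, 2.0, 2.4 and 2.6 it gives 91.5%, 86.1%, 74.0% and 68.1%. The stated table is reproduced.

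**2. Type I error of the choice.** 8,000 null trials per scenario, integer scores 0–10, near-normal (mean 4.98) or right-skewed (mean 2.5), SD 2.2, T1–T3 correlation 0.3 to 0.7:

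| How the test is chosen | Type I error |
|---|---|
| Tie-corrected Wilcoxon, fixed in advance | 9.9–10.5% |
| Skewness check before any group test | 9.6–10.4% |
| Lower p-value of Wilcoxon and t-test | 11.2–13.7% |
| Same, adding a square-root t-test | 13.1–14.8% |

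**3. Ties.** Power of the tie-corrected Wilcoxon test on integer scores with a 1-point shift (near-normal scores) is 80.7%, in line with the stated 80%.

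**4. The 1.0-point rule on a transformed scale.** From 5 to 4: √5 − √4 = 0.236 and ln 6 − ln 5 = 0.182. From 2 to 1: √2 − √1 = 0.414 and ln 3 − ln 2 = 0.405. One PINS point has no fixed size after transformation.

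**5. Ignoring the strata.** Stratified randomization balances the strata across arms, so the real variance of the comparison comes from the within-stratum SD, while the unstratified test refers to the total SD. Keep the total SD at 2.2 and let the strata differ by d: within-stratum variance = 4.84 − 0.6·0.4·d².

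- d = 2.76: 4.84 − 1.83 = 3.01, SD 1.735. The effective critical value is 1.645 × 2.2/1.735 ≈ 2.09, a two-sided level of about 3.7%.
- d = 1.5: 4.84 − 0.54 = 4.30, SD 2.074. The effective critical value is 1.645 × 2.2/2.074 ≈ 1.745, about 8.1%.

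Simulation on integer scores agrees:

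| Gap between strata | Type I error, unstratified | Power, unstratified | Power, van Elteren |
|---|---|---|---|
| 2.76 | about 4% | 84% | 92% |
| 1.5 | about 7–8% | about 81.5% | about 83.5% |

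Type I error of van Elteren was 8.5–10.5%. With no gap, it costs about 1 point of power.

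**The case against.** The strongest reply is that the plan already orders the steps: assumptions first, then a method, then the test. Step 2 supports it. A reader might infer that type I error is uncontrolled, but selection by an assumption check stays near 10%. The 11–15% figures describe keeping the more favourable p-value, which the wording rules out. A reader might also assume that the choice is made with arms visible. Section 13.5 says only that scores are summarized and plotted at each time point. It does not say by arm, or before the method is chosen. What stands is that no rule or blinding backs the stated order.

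A reader might infer that ANCOVA can replace the primary test. The text introduces it as an additional analysis, so that reading is not supported, although its role is undefined. Nor is the 1.0-point rule unusable: a raw PINS difference can be reported beside any p-value, and an untransformed t-test or ANCOVA gives one directly. The gap is that 13.7.2 does not say which figure counts, and it exists without any switch.

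The harm to the efficacy claim can also be overstated. If the rule means Wilcoxon p < 0.10 plus an observed raw mean difference of at least 1.0 favouring Jacki, efficacy is declared in about 0.3–0.6% of simulated null trials. Significance alone needs only about 1.645 × 2.2 × √(2/65) = 0.63 points. This answer depends on a reading that the plan does not state.

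On the strata, it is fair to say that the plan was sized for the unstratified test and reaches its 80% with it. A baseline-adjusted ANCOVA might gain more (89.8% in simulation at an assumed T1–T3 correlation of 0.5), but the documents give no such correlation.

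**Conclusion.** The point holds as a gap in specification and a missed gain in efficiency, not as a demonstrated loss of error control. The primary test should be fixed because the freedom to change it has no criterion and the stated reason, ties, does not call for it. The estimator behind the 1.0-point rule should be named whichever test is used.

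The gain from stratifying depends on the T3 gap between unilateral and bilateral patients: about 8 points of power at 2.76, about 2 at 1.5, and a loss of about 1 at zero. The 2.76 figure comes from a survey taken just before discharge, not at drain removal and not only in patients with reconstruction, so the T3 gap may be smaller. It also fits a total SD of 2.2 only with a within-stratum SD of 1.735, below the survey's 2.13 and 2.28. If the within-stratum SD were 2.2, the total would be √(4.84 + 1.83) = 2.58 and the unstratified level about 5% (critical value 1.645 × 2.58/2.2 ≈ 1.93). The direction is the same and the effect smaller. The number of hospitals is not stated and was also assumed.

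**What to change.** - In 13.5, delete the two sentences that allow the t-test and defer the choice of method.
- State one primary test: Wilcoxon rank sum with midranks and tie-corrected variance, stratified by unilateral versus bilateral mastectomy and hospital (van Elteren), two-sided 0.10. Pool small hospitals by a rule fixed in advance if strata are sparse.
- In 13.7.2, define the difference as the untransformed difference in mean T3 PINS, with a 90% CI.
- Label the t-test and ANCOVA as supportive analyses that cannot change the efficacy conclusion. This matters for ANCOVA because its candidate factors include home pain medication and post mastectomy clothing, which arise after randomization, and the diary's clothing list includes the Jacki itself.

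The cost is wording: no added patients or data, and about 1 point of power if the strata prove not to be prognostic. Naming the estimator also brings out a feature of the existing rule: read as an observed difference of at least 1.0 plus significance by the unstratified Wilcoxon test, it succeeds in only about 48% of simulated trials at the planned 1-point shift (realised mean 0.97 after rounding and truncation). The sponsor should confirm that this is intended.

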Post-operative pain experienced by women undergoing mastectomy and breast reconstruction can contribute to limited range of motion in the upper body, resulting in worsening stiffness and edema that have a negative impact on quality of life (QOL) and activities of daily living (ADL). It is vital that early upper body exercise and movement is performed to prevent lymphedema or swelling.¹² Increased activity can reduce the side effects of surgery, shorten recovery time, and ultimately improve long-term outcomes.^{13,14} This was demonstrated in a study of 35 post-operative mastectomy patients randomized to participate in an early physical rehabilitation program: participants in the program reported significant improvement in pain reduction and QOL.¹⁵ Consequently, studies have demonstrated that inadequately managed pain in the acute post-operative period is one of the greatest predictors of chronic pain syndromes in breast surgery patients.¹⁶⁻²¹

Traditional clothing options for women post mastectomy are undergarments such as post mastectomy camisoles, tank tops, and customized mastectomy bras. Camisoles are usually worn as nightwear or under loose fitting clothing until surgical drains are removed. The Jacki is a post mastectomy garment that was developed by a breast cancer survivor as a means to manage and hold the drainage system. The jacket is professionally manufactured, made with high quality material (cotton and Polartec® microfleece), and is suitable for business casual attire. Anecdotally-reported patient experiences suggest that use of the Jacki immediately after surgery is an early intervention that may reduce pain and prevent activity limitations over time.^{22,23} The Jacki is unique as outer apparel that can be worn in the workplace, at social events, and during usual activity, and that allows full range of motion. The Jacki allows the patient to discreetly place drainage tubes in hidden and secure inside pockets that reduce the possibility of dislodgement and pulling. Velcro sleeves allow for easy access when patients return for follow-up appointments that require taking blood pressure, IV access, injections and medical exams. In particular, women have described²⁴ how the Jacki has put them at ease when in public venues that otherwise would have created feelings of vulnerability and self-consciousness because of body changes and functional limitations from surgery.

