4. REGISTRATION PROCEDURES

4.1 General Guidelines for DF/HCC Institutions

Institutions will register eligible participants in the Clinical Trials Management System (CTMS) OnCore. Registrations must occur prior to the initiation of protocol therapy (i.e., discharge from the hospital). Any participant not registered to the protocol within this timeframe will be considered ineligible and registration will be denied.

A member of the study team will complete the protocol-specific eligibility checklist.

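### The optional ANCOVA in 13.5 adjusts for home pain medication and undefined clothing, both arising after randomization, so its arm coefficient may not estimate the effect of assignment

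*Combined protocol and SAP*

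**What the plan says.** The primary comparison in 13.5 is an unadjusted Wilcoxon rank sum test of the T3 pain score, or a t-test if that is chosen before testing. The sample is participants who are "randomized and have reported a pain score at T3 regardless of intervention use". The section then adds: "Additionally an analysis of covariance (ANCOVA) approach may be considered". The factor list opens with "Factors that may be associated with the T3 pain score (baseline score, time since discharge" and closes with "pain management at home with pain medication, and post mastectomy clothing) will be assessed univariately and then adjusted in a multivariable model". Between these stand unilateral or bilateral surgery, number of drains, neoadjuvant chemotherapy and axillary dissection.

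Section 13.5 does not write out an arm term, define clothing, or say what the arm coefficient would estimate. Section 13.6 asks that secondary analyses at the final time point be consistent with 13.5.

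On timing, 4.1 states: "Registrations must occur prior to the initiation of protocol therapy (i.e., discharge from the hospital". Under 5.1.1 the assignment is received at registration. Section 5.1.3 places medication use and garment wear in the home diary kept between discharge and T3.

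**The concern.** The wording that defines the primary sample implies that the trial asks about the effect of being assigned the jacket. A covariate that assignment can change may carry part of that effect, or may share unmeasured causes with pain. Conditioning on it can then make the arm coefficient estimate something else.

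Clothing is the sharper case, because one natural coding puts the intervention in the model beside arm. Home medication is a plausible second case: less pain can mean fewer pills, and fewer pills can mean more pain.

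At stake is a supportive analysis that could disagree with the Wilcoxon result for reasons unrelated to the effect of assignment. It could travel further. Section 13.6 could carry the same model to the secondary endpoints. Section 13.7.2 asks for a significant difference of at least 1.0 point without saying which analysis supplies the difference, and a rank sum test does not itself give a mean difference.

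**Working it through.** **1. The plan's own figure.** Section 13.2 gives N = 130, difference 1.0, SD 2.2, two-sided alpha 0.10 and 80% power. It does not state the allocation ratio, so I assume 65 per arm. With the Wilcoxon efficiency 3/π, the effective n per arm is 65 × 0.955 = 62.1. Then (1.0/2.2) × √(62.1/2) = 2.53, and Φ(2.53 − 1.645) = 81%, against the stated 80%. The figure is reproduced, and no ANCOVA covariate enters it.

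**2. When each listed factor is determined.**

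| Factor | Determined | Can assignment change it? |
|---|---|---|
| T1 score | In hospital, day 1 or 2 after surgery | Precedes use of the jacket at home |
| Laterality, drains placed, neoadjuvant chemotherapy, axillary dissection | Before discharge | Not through home use of the jacket |
| Home pain medication | T2 diary | Plausibly |
| Post mastectomy clothing | T2 diary | Yes, if Jacki wear is included |
| Time since discharge | Visit when all drains are out | Not shown in the documents |

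**3. What clothing could mean.** Section 2.4 says "Traditional clothing options for women post mastectomy are undergarments such as post mastectomy camisoles, tank tops, and customized mastectomy bras", which supports a bra or camisole coding. The same section says "The Jacki is a post mastectomy garment that was developed by a breast cancer survivor", and the diary's clothing table in Appendix A lists the Jacki with the bra and the camisole or tank top. Both codings fit the text.

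**4. Formula.** In least squares with arm and one covariate C:

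adjusted arm coefficient = unadjusted difference − (arm difference in mean C) × (within-arm slope of pain on C)

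The documents give no wear rates, medication shift or slopes. Everything below is assumed, with the unadjusted difference set at −1.0.

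**5. Clothing coded as Jacki wear.** Assume 80% wear against 0%, wear otherwise unrelated to pain, and a share s of the effect acting through wear. The slope is −s/0.8, so the coefficient is −1.0 − 0.8 × (−s/0.8) = −1.0 + s.
- s = 0, 50% or 100% gives −1.00, −0.50 or 0.00.
- The variance inflation is 3.0. With an assumed T1–T3 correlation of 0.5, the simulated SE rises from 0.34 to 0.60, and at s = 0 power falls from 90% to 52%. That last case is lost precision, not bias.
- If latent wear is correlated −0.3 or +0.3 with residual pain, simulation gives −0.18 or −1.79 at s = 0, and +0.80 or −0.80 at s = 100%.

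**6. Clothing coded as bra or camisole only.** With 40% wear in the Jacki arm, 70% in usual care and no effect on pain, simulation gives −1.01, SE 0.36 and power 89%. The harm is small.

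**7. Home medication.**

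| Shift in use by assignment | Slope of pain on use | Adjusted coefficient |
|---|---|---|
| −0.5 | +0.5 (more use goes with more pain) | −1.0 + 0.25 = −0.75 |
| −1.0 | +0.5 | −1.0 + 0.50 = −0.50 |
| −0.5 | −0.25 (use relieves pain) | −1.0 − 0.125 = −1.125 |
| −1.0 | −0.5 | −1.0 − 0.50 = −1.50 |
| 0 | any | −1.00 |

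The direction depends on why women take the medication, which the documents cannot settle. If assignment does not change use, there is no bias.

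**8. Time since discharge.** With an assumed slope of −0.05 to −0.1 point per day, a 1-day shift moves the coefficient by 0.05 to 0.10, and a 2-day shift by at most 0.20. With no shift it does not move.

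**The case against.** The ANCOVA is additional and optional, its arm term is only implied by the name, and no section rests a conclusion on it. The factors are introduced as possible correlates of pain and screened univariately, which fits a prognostic model where such covariates are legitimate. Secondary objectives 2 and 3 already cover pain management by group and Jacki use. All of this is fair, and it limits the weight of the point. It does not remove it, because 13.5 does not label the model as prognostic or exploratory, and ANCOVA ordinarily names a between-group comparison.

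A reader might infer three stronger things that the documents do not support.
- **That the primary result is compromised.** The Wilcoxon test uses none of these covariates.
- **That the model adjusts the treatment away, or often finds an effect where none exists.** With a true effect of zero, simulated rejection at nominal 10% reaches 39% in the 80% against 0% wear case, but only with Jacki-wear coding and an assumed wear–pain correlation of ±0.3. At ±0.1 it is 13 to 14%, and at zero about 10%. The coding is one of two readings, and the rates and correlations are assumed.
- **That time since discharge is an equal fault.** It is determined after randomization. But 2.4 says only that the jacket has "hidden and secure inside pockets that reduce the possibility of dislodgement and pulling", and 7.1.1.1 lists dislodgement with re-insertion as a potential event. Neither says the jacket changes when drains come out. T3 may fall 7 to 42 days after discharge, so adjusting for it has an evident purpose, and statisticians could differ on it.

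**Conclusion.** The point holds for two covariates, home pain medication and post mastectomy clothing. Both are recorded after assignment, and clothing may include the intervention. If the ANCOVA is run as listed with an arm term, its coefficient may not estimate the effect of assignment.

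The direction is open and the size cannot be derived from the documents; the figures above show only what assumed inputs would do. Harm is small if clothing means bra or camisole only, and absent for medication if assignment does not change its use. Time since discharge is a secondary caution. The primary test, sample size and stated power stand. This should be fixed because a less biased specification is available at the cost of wording, but it concerns a supportive analysis only.

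**What to change.** In 13.5, limit any between-arm ANCOVA to:
- arm, written out;
- T1 PINS;
- the stratification factors in 13.3 (enrolling hospital, which the present list omits, and unilateral or bilateral mastectomy);
- surgical and clinical factors fixed before discharge: number of drains placed, neoadjuvant chemotherapy and axillary dissection.

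Section 5.1.1 describes T1 collection after the step at which assignment is received. The SAP should note that T1 may follow knowledge of the arm, although it precedes use of the jacket at home.

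Remove home pain medication and post mastectomy clothing from this model. Report them by arm under secondary objectives 2 and 3, or in a separately labelled exploratory model that states whether clothing includes the Jacki and that its arm term is not the effect of assignment. If time since discharge is adjusted for, show the result with and without it as a sensitivity analysis. Apply the same restriction wherever 13.6 reuses the model.

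The cost is SAP wording. No new data are needed, and the removed variables are still collected and reported.
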